Administrative data-derived measures include items such as continuity of care, use of the emergency department, hospitalizations, and access to primary and specialty care, timely follow-up after initial prescriptions of ADHD medications or after psychiatric hospitalization.[45,46] We will incorporate recent methodological advances in operationalizing these measures from administrative data.[47] All study measures will be reviewed with our Patient Advisory Panel in order to prioritize the measures determined to be of greatest importance to our patient population. The Patient Advisory Panel may also propose and prioritize additional patient-centered outcome measures during the first two years of the project.

Key treatment variable: The key variable of interest is the enrollment in the ACO by children with disabilities. This “treatment” was assigned to children seen by one of the health care facilities within PFK’s 34-county service area in Ohio beginning in July 2013. Data from PFK-enrolled children prior to enrollment (July 2010 – June 2013) will serve as primary controls, adjusting for age and length of time on Medicaid. Children who were enrolled in Ohio Medicaid with ABD eligibility in other areas of the state will serve as additional potential controls using Medicaid claims data. We cannot use these children as primary controls due to important limitations in the data, namely the inability to attribute children to other ACOs outside the 34 county PFK region. PFK’s unique arrangement with the state allows us to clearly identify the ACO catchment area by county and thus we can clearly attribute these patients to PFK.

Patient Characteristics: Our analysis is conducted on a diverse population of children and adolescents. Their characteristics vary by age, gender, race, Latino ethnicity, SSI status, county of residence, diagnoses, procedures received, length of time on Medicaid and other patient characteristics as detailed in **Appendix F**. We will create baseline disease adjustment categories using the Chronic Illness and Disability Payment System, which was specifically designed for disabled Medicaid enrollees. [48]

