The underlying population for this study is all children up to age 18 enrolled in the Partners for Kids (PFK) on May 30th 2015 who had been previously enrolled in fee-for-service (FFS) Medicaid and transitioned into PFK as a result of the ABD policy change. The primary analytic data comes from Ohio Medicaid administrative claims. Claims data have different missing data issues than do other primary or even secondary data sets on several dimensions. First, many of the fields are mandatory, which means fields such as procedure code and Medicaid eligibility status will

be 100% complete. Second, although claims data have the traditional limitations of any administrative data, including the lack of information of services paid fully out-of-pocket or financed through Medicare, only services provided through Medicaid will be used in the analysis, which will take a Medicaid/agency perspective. This means that services and expenditures will not aim to be a complete record, but those covered through the Medicaid program. We will clearly indicate the scope of analysis in publications. For the subsets of claims data merged with survey and medical records, we do not anticipate missing data problems for the same reasons above.

The estimated size of this population is 8,000. Because of the qualitative nature of Aim 1 we do not propose a missing data plan. The following assumptions have been made regarding rates of participation from this population for Aims 2 and 3:

Aim 2 – Caregiver Survey

We expect 34% percent of the eligible caregivers to complete the caregiver survey. This is based on assumptions from previous studies with this population regarding degree of incorrect addresses for the opt-out mailing, opt outs, missing/non-functional telephone numbers, and refusal when contacted.

- *Prevention of missingness*– We will use alternative sources of contact information (e.g. EHR records, internet look-up sites) for those families with missing telephone numbers.
- *Monitoring of missingness* – we will record and report the following statistics: % of invitation letters returned by the post office, % opting out, % bad telephone numbers that cannot be found after research, and % refusal by reached families. For each of these percentages, we will describe the lost respondents by gender, age, urban/rural residence, and diagnosis category using PFK data (note: race is not reliably available on the PFK data).

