We expect 35% percent of those completing the telephone survey to consent to medical record abstraction.

- *Prevention of missingness* – The script requesting medical record access will clearly explain the reason for access and the processes for maintaining confidentiality.
- *Monitoring of missingness*– We will describe the lost respondents by gender, age, urban/rural residence, and diagnosis category using claims data. We will also test the relationship between perceptions of care coordination and consent to medical record abstraction using data from the telephone survey.

A consort-style diagram will be used to illustrate potential participant loss or refusal at each stage of the study **(MD-4)**.

Aim 3 – Utilization Analysis

Over 95% of the population will be included in claims data analysis looking at overall pre-/post-policy change utilization analysis. The primary risk of missingness for this analysis is failure of successful linking between the FFS (pre) and PFK (post) data. After acquisition of the data, we will first assess the data quality. Like the traditional Medicaid plan, PFK reimburses physicians

on the basis of services provided (fee-for-service), therefore we expect that the payment data and other fields such as patient id, date of service, and procedure codes required for reimbursement will be populated for each claim billed to Medicaid/PFK. The demographic files (e.g. gender, race) may also have missing data, which is anticipated to be proportionally small, based on the team's prior experience with claims.

- Prevention of missingness – We will investigate each non-match. When there is no matching Medicaid ID across the two databases, we will directly check the record to identify potential transposition or typographical errors. If no such error can be found, we will attempt to use probability matching using date of birth, zip code of residence, gender, and soundex last name to link records.
- Monitoring of missingness– We will calculate and report the final “no-match” rate between PFK and state FFS data.

Statistical methods and sensitivity analysis to handle missing data (MD2, MD3, MD5)

Aim 2 – Caregiver Survey

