Methods for statistical handling of missing responses on the Family Experiences of Care Coordination survey are documented in the survey's scoring guide. We will use these methods to assure that our results are consistent with those being generated in other implementations of the survey. Missing data will not be imputed, however, we will use sensitivity analysis to estimate the effect of differential non-response by age, gender, urban/rural residence, and diagnosis category. We do not hypothesize differential missingness.

Aim 3 - Utilization Analysis

The pre-/post-policy change utilization analysis will be performed on all individuals where we are able to link FFS and PFK claims. We expect a low non-link rate. However, to estimate the impact of the missing data, we will conduct sensitivity analysis by testing change in setting-specific utilization if all the unlinked cases were at the 90th percentile of their age/gender/diagnosis category group and if all unlinked cases were at the 10th percentile of their age/gender/diagnosis category group.

For time invariant missing variables in the FFS or PFK data, such as gender or race, we will carry the last observation forward, assuming gender and race is unchanged for each individual. In the rare case of substantial amount of other types of missing data in the claims, we will employ Multiple Imputation (MI) methods to generate imputations for the missing values, from predicted probabilities estimated based on the complete data (observed and missing data).

Procedures

Aim 1

In all aspects of Aim 1, we will use purposive sampling, attempting to get a mix of participants and to maximize the diversity of our sample in terms of perspectives that we expect to be

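### For outcomes that fewer than 10% of a cell experience in the period, both percentile scenarios for unlinked children impute zero, so high use goes untested

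*Combined protocol and SAP*

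**What the plan says.** The methods part of the missing-data plan (MD2, MD3, MD5), under Aim 3 - Utilization Analysis, runs the pre/post comparison on children whose claims can be linked. It then adds one sensitivity analysis, "testing change in setting-specific utilization": first "if all the unlinked cases were at the 90th percentile of their age/gender/diagnosis category group", then "if all unlinked cases were at the 10th percentile of their age/gender/diagnosis category group". No separate rule is given for outcomes that are mostly zero.

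The MD-1 part of the same plan explains why this check matters: "The primary risk of missingness for this analysis is failure of successful linking between the FFS (pre) and PFK (post) data". The expected size of the problem is given only indirectly. The plan says "Over 95% of the population will be included in claims data analysis" and "We expect a low non-link rate", and for the population, "The estimated size of this population is 8,000".

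The claims-derived outcomes listed in the main Aim 3 text include "use of the emergency department, hospitalizations, and access to primary and specialty care". Measures are to be quarterly and annual as appropriate (Outcomes Measures), and the data will be supplied by person-month (Procedures, Aim 3, Assumptions).

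Three things are not stated: the period over which the percentile is taken; whether the fee-for-service period, the PFK period or both are imputed; and whether the percentile is of the level of use or of the within-child change.

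**The concern.** A pair of low-use and high-use scenarios is informative when the two lie on either side of the observed value. Percentiles do this for a continuous or frequent measure. They do not for a count or indicator that is zero for more than 90% of a cell, because the 10th and 90th percentiles are then the same number, zero. The scenario meant to represent heavy users assigns them no use at all.

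The risk is one of interpretation. Two agreeing scenarios will be read as evidence that link failure does not matter, when the possibility that unlinked children are heavy users was never examined. This is the only planned sensitivity analysis for what the plan itself calls the main missing-data risk in Aim 3, and hospitalizations are among the outcomes it has to serve.

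**Working it through.** The plan gives no computed result for this analysis, so there is no figure to reproduce. The check applies the rule directly.

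**Inputs from the documents**
- Rule: each unlinked child takes the 90th, then the 10th, percentile of its age/gender/diagnosis cell.
- Unlinked share u: under 5%, inferred from the statement that over 95% are included. With 8,000 children this is at most about 0.05 × 8,000 = 400.

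**Assumptions**
- The share p of a cell with at least one event in the period is not in the documents, so a range is used.
- One event per user, u the same in every cell, and independence between periods when converting annual to shorter periods.

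**Step 1: when the percentiles are zero.** The 10th percentile is 0 if p < 0.90. The 90th percentile is 0 if p < 0.10.

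**Step 2: effect in one cell.** Rate after imputation = (1 − u) × observed rate + u × percentile value. With u = 5%, per 1,000 children:

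| Observed | 10th-percentile scenario | 90th-percentile scenario | 90th vs observed |
|---|---|---|---|
| 30 | 28.5 | 28.5 | −5% |
| 50 | 47.5 | 47.5 | −5% |
| 80 | 76.0 | 76.0 | −5% |
| 120 | 114.0 | 164.0 | +37% |
| 150 | 142.5 | 192.5 | +28% |

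For example, at 50 both scenarios give 0.95 × 50 + 0.05 × 0 = 47.5. At 120 the high scenario gives 0.95 × 120 + 0.05 × 1,000 = 164. Below the threshold the fall equals u, so it is 1% at u = 1% and 2% at u = 2%. The sign changes at p = 10%: with u = 5%, 99 per 1,000 becomes 0.95 × 99 = 94, whereas 101 per 1,000 becomes 0.95 × 101 + 50 = 146.

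**Step 3: dependence on the period.** The 90th percentile is 0 when the annual share with an event is below:
- annual measure: 10%
- quarterly measure: 1 − 0.9^4 = 34.4%
- person-month: 1 − 0.9^12 = 71.8%
- three-year window (such as July 2010 to June 2013): 1 − 0.9^(1/3) = 3.5%

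**Step 4: cells that differ.** The rule works by cell and the result is pooled. Cells were simulated with annual prevalence drawn from a beta distribution (mean 5%, parameters summing to 6) and u = 5%. Rates are per 1,000:

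| Period | Cells with 90th percentile 0 | Observed | 10th | 90th |
|---|---|---|---|---|
| Annual | 83% | 51.1 | 48.5 | 57.2 |
| Quarter | 98% | 13.2 | 12.5 | 13.4 |
| Month | 100% | 4.7 | 4.4 | 4.4 |

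So the pooled range collapses entirely on person-months. On quarters the high scenario stays close to the observed rate. On annual measures it keeps a usable upper scenario, supplied by the minority of cells above 10%.

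**Step 5: effect on the pre/post comparison.** If only the pre-period is imputed and every cell gives 0, the post/pre ratio is inflated by at most 1/0.95 = 1.053.

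**The case against.** The strongest reply is that the failing condition is not shown to occur. The documents give no admission or emergency department rates for these children, who are disabled and cost $1,188 a month against $205 for other Medicaid children, so some diagnosis cells may well exceed 10%. The percentile's period is unstated too, and on annual or three-year windows the 90th percentile could be 1 or more in many cells. This stands. It is why the point is conditional, with admissions by quarter or person-month as the likely case rather than a demonstrated one.

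A reader might infer that the high scenario always lowers the rate, or that the analysis can only point one way. The documents do not support that. The rule is applied by cell, and Step 4 shows that a few high-use cells can lift the pooled high scenario above the observed rate. If the percentile is of the within-child change, imputing zero pulls the change toward zero rather than lowering a rate.

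A reader might also extend the point to follow-up after psychiatric hospitalization. That measure is a proportion among discharged children and need not be rare. If between 10% and 90% receive follow-up, the percentiles are 0 and 1 and do bracket the observed value.

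Finally, the analysis is secondary, non-matches are first pursued by record checks and probability matching, and the no-match rate will be reported. All true, and it limits the size of the effect. It does not make two identical zero scenarios informative.

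**Conclusion.** The point holds in conditional form and is minor. In any cell where fewer than 10% have the event in the period, the stated rule imputes zero in both scenarios, so they coincide below the observed mean. That follows from the rule alone. That it will affect quarterly or person-month admissions rests on an assumption, though an undemanding one: annual admission shares below about 34% or 72% of a cell, with independent periods.

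Where nearly all cells are zero, the pooled high scenario falls short of the observed rate by at most about 5%, and by less if fewer children are unlinked. Just above 10% the scenario overshoots instead, so its direction depends on which side of a threshold the cell falls and not on any view of how unlinked children differ. The primary estimate is untouched. So are outcomes that well over 10% of each cell experience.

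**What to change.** In the Aim 3 paragraph of the missing-data methods:

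1. State the period over which the percentile is taken, which period is imputed (fee-for-service, PFK or both), and whether it applies to the level or the change.
2. For outcomes with under 10% prevalence in a cell, replace the percentiles with multiples of the cell mean rate, for example 0.5 and 2, labelled as illustrative. The pooled rate is then observed × [1 + u(k − 1)] for multiplier k. At 50 per 1,000 and u = 5% this gives 50 × 0.975 = 48.75 and 50 × 1.05 = 52.5, which bracket the observed value without a jump at 10%.
3. Report a tipping-point multiplier: the value of k at which the level or trend change loses significance.

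Percentiles may stay for expenditures and common outcomes. The cost is a few sentences and a little more programming, with no new data. The downside is that the multipliers are a judgement with no basis in the documents, which is the reason for adding the tipping point.

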- The ACO (PFK) mails letters to potentially eligible enrollees describing the study and offering them the option of opting out of the sampling frame. Contact information for those who do not opt out will be sent to CSRL for survey contact.
- CSRL will send letters to all non-opt out families. The letter will include thanks for willingness to participate, telephone survey logistics, and a web address that can be used to complete the survey on their own. We expect up to five percent of respondents to use the web-based survey.
- Trained interviewers will make up to 10 telephone attempts for each caregiver who does not complete the online survey. When telephone numbers are found to be non-functional, research staff will make reasonable efforts to find working numbers through use of Lexus-Nexus and through working with PFK staff with access to electronic medical record (EMR) information that may offer updated contact information.
- Surveys will be conducted using a computer-assisted telephone interviewing (CATI) system with interviewer performance monitored through review of randomly selected taped interviews.
- Prior to the close of the interview, the interviewer will request verbal consent for a review of care coordination documentation in their medical records and for linking of their survey responses to medical record and claims data.
- All individuals who complete the interview will be mailed a \$20 gift card in appreciation of their participation.

Key Decisions

- We will keep the survey wording the same because it has been field tested and underwent cognitive development testing.
 - It is not necessary to allow for N/A (for e.g. 5E – needing equipment, in all the piloted work this was never an issue).
 - Refusals or don't know – they may not be read, but interviewer can fill it in. If subject says they don't know, record in notes and leave unanswered or say respondent refused. For programming purposes, refuse/don't know is a (non-read) option. Email-based surveys can allow blanks (in fact are mandated to allow).
- Web survey
 - We will pilot the web survey.
 - CSRL will do in-house.
 - We will also pilot with Patient Advisory Panel prior to April 6th patient advisory panel meeting.
 - We will work on web survey first to make sure it is available for pilot testing, and then focus on the phone survey.

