ATTACHMENT B

Detailed Measure Specifications and Scoring for FECC Caregiver Survey Indicators

All are on 0-100 scale, where higher is better. Survey response items should be coded to reflect that. For dichotomous items, "no" = 0 and "yes" = 100. More specific instructions are included where applicable in Scoring Notes.

All screener items must be nonmissing for a dependent item to be scored

If items are part of a yes/no checklist, if at least one item is answered, impute "no" for skipped items in mailed surveys or "don't know" for telephone surveys (but not for items that telephone respondents refused to answer).

Otherwise, all component items must be nonmissing for a multi-item indicator to be scored.

MP=Main Provider

Indicator ID	Indicator Description	Eligible	Survey Item	Scoring notes
CARE COORDINATION SERVICES				
CC2	Caregivers should report that their child has a designated care coordinator.	Q2=1 (Child visited more than one doctor's office or used more than one kind of health care service in last 12 months)	Q3 (Someone in MP's office helped manage child's care or treatment from different doctors/providers)	
CC3	Caregivers who report that their child has a designated care coordinator (as identified in CC2) should report that they know how to access their care coordinator.	Q2=1 (Child visited more than one doctor's office or used more than one kind of health care service in last 12 months), Q3=1 (Someone in MP's office helped manage child's care or treatment from different doctors/providers)	Q6 (Knew how to contact person who helped manage child's care when you needed help or had a question)	
CC5	Caregivers who report having a designated care coordinator (as identified in CC2) and who require community services should also report that their care coordinator helped their child to obtain needed community services in the last year.	Q2=1 (Child visited more than one doctor's office or used more than one kind of health care service in last 12 months), Q3=1 (Someone in MP's office helped manage child's care or treatment from different doctors/providers), Q15=1 (Caregiver or child needed or used community services in last 12 mos)	Q16(Person in MP's office who helped manage child's care helped get community services)	

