IE3c	Was useful	Q20	
IE4	Caregivers should report having been invited to join in hospital rounds during their child's last hospitalization	Q21=1 (child had overnight hospital stay in last 12 mos)	Q25 (Last time child was in hospital, invited to take part in hospital rounds)
IE5	Caregivers/patients should report receiving a written visit summary of their child's last hospitalization at the time of discharge, and they should report the summary contained the following elements:	Q21=1 (child had overnight hospital stay in last 12 mos), Q22=1 (Last time child was in hospital, got written hospital stay summary at discharge)	Q23 (Did written hospital stay summary include...) Mean of IE5a-f
IE5a	Problem list at time of discharge	Q23a	
IE5b	Medication list at time of discharge	Q23b (Rx), Q23c (OTC)	Mean of rescaled Q23b and Q23c
IE5c	Drug allergies		Q23d (list of "child's allergies", not drug allergies specifically)
IE5d	Specialists involved in the child's care during the hospitalization		Q23e
IE5e	Planned follow-up		Q23f
IE5f	What to do for problems related to the hospitalization		Q23g
IE6	Caregivers who received a written summary of their child's hospitalization at discharge (as	Q21=1 (child had overnight hospital stay in last 12 mos), Q22=1 (Last time child was in	Q24 (Hospital stay summary easy to understand)

described in indicator IE5) should report that the information contained in the visit summary was easy to understand hospital, got written hospital stay summary at discharge)

MH3a	Caregivers should report having access to an electronic health record to look up information about their child's visits and health care.	All caregivers of children with medical complexity	Q26 (In last 12 mos, MP's office had web site or app caregiver could use between visits to look up information about child's visits and care)	If Q26=1 (Yes): 100 points If Q26=2 or 3 (No or Don't Know): 0 points
MH3b	Caregivers who report having access to an electronic health record should also report that it includes the following health information:		Q26=1 (In last 12 mos, MP's office had web site or app caregiver could use between visits to look up information about child's visits and care)	Do not score the N/A's; If no immunizations (meds), do not score MH3b1 (MH3b2); If didn't look at med list, do not score MH3b2 Take mean of MH3b1 and MH3b2

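### Telephone 'don't know' answers are to be left blank or called refusals, but the adopted FECC scoring guide needs the two kept apart; IE5 is the indicator most likely affected

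*Combined protocol and SAP*

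**What the plan says.** **Collection.** In the combined protocol and SAP, Procedures, Aim 2, Caregiver Survey Methodology, Key Decisions, the interviewer may enter a refusal or don't know without reading it out. For a respondent who does not know, the instruction is to "record in notes and leave unanswered or say respondent refused". The same bullet adds: "For programming purposes, refuse/don't know is a (non-read) option". No item is exempted. The survey steps in that section state: "We expect up to five percent of respondents to use the web-based survey".

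**Scoring.** The Aim 2 part of the section on statistical methods for missing data adopts the survey's scoring guide, so that results match other implementations. It then says that missing data will not be imputed. Attachment B gives the guide's rules:
- The checklist rule begins "If items are part of a yes/no checklist, if at least one item is answered". It then turns skipped items in mailed surveys, and don't-know items in telephone surveys, into no.
- It carves out refusals: "for telephone surveys (but not for items that telephone respondents refused to answer".
- Failing that, "all component items must be nonmissing for a multi-item indicator to be scored".

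**IE5.** The survey item is "Q23 (Did written hospital stay summary include", with parts a to g. The score is the mean of six elements; Q23b and Q23c are averaged to form one of them.

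**The concern.** The guide treats a telephone don't know and a telephone refusal in opposite ways, while the interviewer instruction sends a don't know to a blank or to a refusal. Neither is the code that the guide acts on. Unless someone recodes before scoring, a checklist indicator that the guide would score becomes unscored, and the available-case rule in the Aim 2 Analysis section drops that child from analyses of it.

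Two things are at stake. The stated reason for adopting the guide, consistency with other users of the survey, fails for any affected indicator, and so does the planned comparison with pilot data where that indicator is used. The indicator would also be estimated on a subset selected by how much the caregiver could recall. Nearly all data are exposed: with at most 5% of the expected 2,750 responses by web, at least 0.95 × 2,750 ≈ 2,612 come by telephone.

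**Working it through.** The plan gives no figure for this point, so the check compares the rules and then works an example.

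**1. Follow one telephone don't know on a checklist item, with other items answered.**

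| How it is recorded | What Attachment B does | Indicator |
|---|---|---|
| Don't know | Imputes no | Scored |
| Refused | Expressly not imputed | Unscored |
| Blank | Not a recorded don't know; the skipped-item clause is for mailed surveys | Unscored |

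The last two rows read the all-components rule as covering any checklist item that stays missing. The instruction allows only those two rows.

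**2. Which indicators are checklists?** Attachment B labels none. Of the lettered lists, Q5a-e (CC10) and Q18a-g (IE2) carry graded partial credit. Q23a-g (IE5) asks whether the summary included each element and has no partial-credit note, which fits yes/no scoring at 0 or 100. This is an inference. The word 'rescaled' beside Q23b and Q23c does not settle it, because the graded pair Q18b and Q18c has the same note.

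**3. Worked IE5 case: yes to all items except one don't know.**
- Don't know on an item that forms its own element: guide score = 5 × 100 / 6 = 83.3.
- Don't know on Q23b or Q23c: that element is 50, so (5 × 100 + 50) / 6 = 91.7.
- Under the instruction without recoding: unscored in both cases.

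**4. Share of IE5 scores lost (illustration).** Let d be the don't-know rate per item, which is assumed, and K the number of don't knows among seven items, with no refusals. A child with K = 7 is unscored under the guide too, so the loss is P(1 ≤ K ≤ 6). The mean of K is 7d. If no child has K = 7, the loss lies between 7d/6 and 7d. It falls toward 0 if the don't knows pile up as K = 7. For clustering within a child, use a beta-binomial with a = d(1−ρ)/ρ and b = (1−d)(1−ρ)/ρ; the loss is 1 − P(0) − P(7). At d = 2% and ρ = 0.3, a = 0.0467, b = 2.2867, P(0) = 0.929 and P(7) = 0.0005, so the loss is 7.0%.

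| d | 7d/6 to 7d | ρ = 0.5 | ρ = 0.3 |
|---|---|---|---|
| 1% | 1.2 to 7% | 2.4% | 3.6% |
| 2% | 2.3 to 14% | 4.8% | 7.0% |
| 5% | 5.8 to 35% | 11.5% | 16.7% |

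**5. Bias.** With share f lost, bias = f × (mean of kept − guide mean of dropped). A dropped child scores at most 91.7 under the guide, but the kept mean is unknown. Upward bias is therefore certain only if the kept mean exceeds 91.7. For scale, f = 5% and an assumed gap of 20 points in either direction give 1.0 point. If 10 to 30% of 2,750 respondents are eligible for IE5 (assumed; n = 275 to 825), the worst-case 95% half-width, 1.96 × 50/√n, is 5.9 to 3.4 points.

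**The case against.** - **The distinction may survive.** The option quoted above could be one code or two, and a blank accompanied by a note can still be recognised as a don't know. The analysis is also committed to the guide. This is fair, and it means the information is probably recoverable. However, even with two codes the instruction directs the interviewer to a blank or a refusal, and no step in the text turns notes back into codes.
- **IE5 is not labelled a checklist.** This is correct. If the instrument shows otherwise, the guide itself would leave IE5 unscored and the discrepancy there would vanish. The questionnaire's response codes are not in the text available to me, so the absence of a recoding step there is only weak evidence.
- **The effect is small.** It may be. The Aim 2 Analysis section expects limited missing data, and the illustrative bias is below sampling error. The lost scores and the departure from the adopted rule remain.

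A reader might also infer that MH3a, MH3b, MH6 and SCP4 are inflated, because they score a don't know as zero. The documents do not support this: Q26, Q27, Q28, Q34 and Q37 have their own numbered Don't Know responses, and the protocol says "We will keep the survey wording the same because it has been field tested". Nor does the no-imputation sentence plainly contradict the guide. Coming after the guide's adoption, it most naturally means no imputation beyond the guide, and needs only a clarifying clause.

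**Conclusion.** The point holds as a conflict between a collection instruction and an adopted scoring rule. Taken literally and without recoding, the instruction leaves unscored some telephone checklist indicators that the guide would score. IE5 is the probable case, subject to confirmation that Q23a-g is a yes/no checklist.

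The size cannot be fixed from the documents. The loss figures rest on assumed don't-know rates and clustering. It is tempting to conclude that IE5 would be biased upward, since dropped children carry at least one imputed no. That follows under a model of independent items, but not in general, so the direction is open as well.

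The reach is limited to Aim 2 checklist indicators and linked analyses that use them. IE5 is one of 31 planned measures, the discharge-summary example in the Aim 2 Analysis section is closer to IE6, and the Aim 3 pre/post claims comparison is unaffected. The change is worth making because it costs little and restores the comparability that the plan claims.

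**What to change.** - Hold separate codes in the telephone system for don't know, refused and blank, and delete the part of the instruction that sends a don't know to a blank or a refusal.
- Confirm from the instrument which items are yes/no checklists (probably Q23a-g), and score them by Attachment B.
- Confirm that the native Don't Know responses on Q26, Q27, Q28, Q34 and Q37 are kept.
- Amend the no-imputation sentence to say that data are not imputed except as the scoring guide specifies.
- If fielding is complete, recode don't knows from the interviewer notes before scoring, and report the share that cannot be resolved.

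The cost is minor programming, one line of interviewer training and one clause of SAP text, or staff time for recoding if the survey is finished. No new data collection is needed.
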